1 INTRODUCTION

The identification of novel targets in malignant tumors has led to the development of inhibitors for the treatment of a wide range of cancers. The rationale for targeting dysregulated pathways has led to the development and testing of several targeted agents. The challenges of developing rational targets for therapeutic intervention in specific solid tumors remain an area of intense research. The current study will evaluate the impact targeting two dominant pathways, hormonal regulation and mTOR, has on endometrial cancer growth in women with recurrent and progressive disease.

1.1 Endometrial Cancer

Endometrial cancer is the most common gynecologic malignancy in the United States with 40,100 new cases and 7,470 deaths estimated for 2008.¹ The standard treatment for primary endometrial cancer consists of a total hysterectomy with bilateral salpingo-oophorectomy and possible lymph node dissection. This may be followed by radiation therapy depending on tumor histology, grade and stage. Treatment failure in low-risk patients is exceedingly rare². Tumor recurrence is most common in women with advanced-stage disease or those with high risk features in their primary tumor³. The patterns of recurrence depend on the initial disease distribution. Women with advanced primary disease tend to have abdominal or systemic failure. In women whose primary disease was limited to the uterus, one third tend to have recurrences limited to the pelvis and two thirds have distant failure. Women with isolated pelvic recurrences can potentially be salvaged with radiation therapy or radical surgery. However, in women with distant recurrent disease, treatment is largely palliative.

1.2 Treatment of Recurrent or Advanced Endometrial Cancer

Several chemotherapeutic agents or combinations of agents have been studied in the treatment of women with recurrent or advanced endometrial cancer. Doxorubicin was one of the first agents identified to have activity in endometrial cancer and treated patients had a 22% response rate and a progression free survival of 3.2 months⁴. Single agent cisplatin and carboplatin when used as first-line agents have also been shown to have anti-tumor activity, with response rates of 20-42% and progression free survival rates of 3-5 months^{3,5,6}. A phase III study combining cisplatin with doxorubicin showed improved progression-free survival but no difference in overall survival⁷. Paclitaxel has also been shown to have activity in endometrial cancer and has been incorporated into combination therapy regimens. The Gynecologic Oncology Group (GOG) is currently performing a phase III study comparing doxorubicin/cisplatin/paclitaxel to carboplatin/paclitaxel.

In addition, some endometrial cancers are hormonally sensitive. Treating recurrent and progressive tumors with progestins and progestins in combination with tamoxifen (a selective estrogen receptor modulator) has had limited results. In a phase II study by the Gynecologic Oncology Group, an aromatase inhibitor (anastrozole) had limited activity as a single agent against recurrent and progressive endometrial cancer. In this study, of the 23 patients enrolled, 2 had partial responses and 2 had short-term stable disease.

Although response rates have improved, more effective systemic agents with longer durations of response are needed. Prognosis remains very poor for patients who fail first-line chemotherapy for progressive or recurrent endometrial cancer ^{3,8}.

1.3 PTEN/AKT/mTOR Pathway:

PTEN, a tumor suppressor gene, has been shown to play several roles in tumor suppression, including cell cycle arrest and promotion of apoptosis. Inactivating mutations in PTEN occur frequently in many human cancers. In particular, mutations in PTEN occur in 80% of endometrial carcinomas.³

Tumor cells lacking PTEN contain high levels of activated Akt. This suggests that PTEN is necessary for the appropriate regulation of the phosphatidylinositol 3-kinase/Akt pathway. Recent studies have identified the AKT kinase as a potential mediator of tumorigenesis in endometrial cancer cell lines.^{3,9} The finding of PTEN mutations in the majority of endometrial cancer suggests that the loss of PTEN function may be one mechanism by which AKT activity is increased in this disease. Because PTEN-deficient cancer cells may have upregulated activity of the mammalian target of rapamycin (mTOR), which is downstream of AKT, these cells may be sensitive to mTOR inhibition.^{10,11}

1.4 RAD001 (everolimus)

RAD001 (everolimus) has been in clinical development since 1996 in solid organ transplantation. Since 2003, the drug is approved in several countries, including the majority of European Union states, as prophylaxis of rejection in renal and cardiac transplantation in combination with cyclosporin A and glucocorticosteroids. Its first commercialization (as Certican) dates from March 2004 in Germany.

Everolimus 5mg and 10mg tablets were recently approved under the trade name Afinitor® for patients with advanced renal cell carcinoma (RCC) after failure of treatment with Sutent® (sunitinib) or Nexavar® (sorafenib) in the US, EU and several other countries and is undergoing registration in other regions worldwide.

The following is a brief summary of the main characteristics of RAD001. Fuller information can be obtained from the [Investigator's Brochure].

[figure not shown]
1.4.1 Pharmacology of RAD001

RAD001 (INN: everolimus) is a novel macrolide formulated for oral administration, which is being developed as an antiproliferative drug with applications as an immunosuppressant and anticancer agent.

At the cellular and molecular level, RAD001 has the same mechanism of action as an immunosuppressant and as an anti-tumor agent. It acts by selectively inhibiting mTOR (mammalian target of rapamycin), an intracellular protein kinase implicated in the control of cellular proliferation of activated T-lymphocytes or neoplastic cells. TOR is a ubiquitous protein kinase implicated in cell cycle control and specifically in the progression of cells from the G1 to S phase. TOR is considered to be a downstream

component of the PI3/Akt pathway, its own primary downstream substrates being the eIF-4E-binding protein (4E-BP1) and p70 S6 kinase 1 (S6K1) which both play a role in the translational regulation of mRNAs encoding proteins involved in G1-phase progression (see Figure 1-1).

Figure 1 RAD001 as an inhibitor of cellular proliferation

GF: Growth factor; PI-3 kinase: Phosphoinositide 3-kinase; FKBP-12: FK506-binding protein 12; 4E-BP1: eIF-4E binding protein 1; mTOR: mammalian “Target of Rapamycin”. Upper Panel: situation in presence of growth factors (mTOR pathway and translational machinery are induced; cells proliferate). Lower Panel: situation in presence of RAD001 (mTOR pathway is inhibited by RAD001/FKBP-12 complex [large X]; translational machinery is inhibited and cells are blocked or delayed in G1 resulting in a block/reduction of proliferation [small X]).

RAD001 acts on interleukin and growth-factor-dependent proliferation of cells through high affinity for an intracellular receptor protein, the immunophilin FKBP-12. The resulting FKBP-12/RAD001 complex then binds with mTOR to inhibit downstream signaling events.

In vitro studies have shown that RAD001 can inhibit the proliferation of numerous cell lines originating from solid tumors, including breast cancer, with the most sensitive cell lines having IC50's at the sub nanomolar/low nanomolar level. In addition, experiments in vitro with human umbilical endothelial cells (HUVECS) and in animal models of angiogenesis suggest an additional anti-angiogenic effect, presumably through mTOR

inhibition in proliferating endothelial cells.

In vivo studies in rodent models have shown orally administered RAD001 to be a potent inhibitor of tumor growth at well-tolerated doses. This has included several different mouse xenograft models, including pancreatic, colon, epidermoid (including a Pgp-170 over expressing, cytotoxic-resistant variant) and two syngeneic models (CA20948 rat pancreatic, B16/BL6 mouse melanoma). In general, RAD001 was better tolerated in mouse xenograft models than standard cytotoxic agents (i.e. doxorubicin and 5-fluorouracil), while possessing similar antitumor activity. Only one instance of in vivo resistance has been observed (MAXF 401 mammary xenograft model), otherwise the activity of RAD001 was general inhibition of tumor growth (persistent regressions in one tumor model, T/C values of 9 to 45% in 12 tumor models). Xenograft models sensitive to RAD001 treatment included tumors derived from cell lines exhibiting comparative resistance in vitro (KB-31 and HCT116).

The preclinical studies also demonstrated that inhibition of p70S6kinase 1 (S6K1), downstream of mTOR, was a marker of drug activity. In vitro, short-term exposure to RAD001 led to S6K1 inactivation for as long as 120 hours. In vivo, in the rat syngeneic setting, a single dose of RAD001 led to S6K1 inhibition for up to 72 hours in tumors and skin and for up to seven days in peripheral blood mononuclear cells (PBMCs).

1.4.2 Clinical pharmacology of RAD001

RAD001 is administered orally, its bioavailability being estimated at approximately 11%. Absorption is intestinal. Absorption is delayed moderately by food (60% reduction in C_{max} and 16% reduction in AUC when drug administration follows a fat-rich meal). The AUC is consistently dose-linear with moderate inter-patient variability (CV approx 50%). C_{max} is dose-linear until 20mg increasing in a non-linear manner thereafter. The terminal half-life is 30-35 hours. The main elimination route for RAD001 is by hepatic metabolism, mainly hydroxylation. The parent compound is the major component in the blood. Metabolism to rapamycin is of minor importance. The main metabolites are not bioactive. Excretion is (>80%) through the bile and the intestinal tract.

RAD001 is a substrate of the CYP3A4 isoenzyme and P-gp and its metabolism is sensitive to 3A4 inhibitors/inducers. In combination with microemulsion cyclosporine A (Neoral®), a 3A4 and P-gp inhibitor, the bioavailability of RAD001 is significantly increased: for AUC by a mean of 168% (range: 46-365%); for C_{max} by 82% (range: 25-158%). RAD001 itself does not appear to have an enzyme-inducing/inhibiting effect at the levels achieved in solid organ transplantation and current oncology studies. Mild-moderate hepatic impairment will increase exposure. Ethnic differences exist with clearance in blacks approximately 20% higher than that in Caucasians and Japanese patients who appear to be similar as regards clearance. Renal function has only marginal influence on the clearance of RAD001 so that no dosage adjustment is necessary in patients with renal failure.

1.4.3 Clinical experience with RAD001 in non-oncology indications

There is extensive safety data on RAD001 because of the advanced stage of its development in solid organ transplantation. Safety data includes animal testing, single-dose studies in non-transplant patients, and short- and long-term studies in transplant patients where RAD001 was administered daily as a part of an immunosuppressant, multi-drug regimen consistently including cyclosporin A and glucocorticoids, and other drugs (azathioprine, basiliximab) on occasions. Controlled studies in the transplant setting consisted of dosage comparisons and comparisons between RAD001 and mycophenolate mofetil or azathioprine, but never placebo, as additions to cyclosporin and steroids.

The tolerability of RAD001, when used alone and given daily, appeared to be good with only mild to moderate suspected adverse drug reactions, mostly headache. Treatment with RAD001, given daily, has been associated with a decrease in absolute neutrophil counts and platelet counts. This is most likely due to a pharmacodynamic action on hematopoiesis. This rarely led to severe leucopenia or thrombocytopenia, defined in the transplant setting as CTC grade 2. Chronic treatment with RAD001, given daily is associated with an increase in serum lipid levels. Hyperlipidemia responded to lipid-lowering drugs. Long-term treatment with RAD001 was associated with reduced testosterone levels, probably the result of interference with sterol metabolism. This did not appear to translate into increased sexual dysfunction. Long-term RAD001 treatment of renal transplant patients with RAD001 and cyclosporin A was associated with an increase in renal dysfunction in comparison with comparator drugs (azathioprine, mycophenolate mofetil) combined with cyclosporin A. The preclinical findings and effects observed on reducing cyclosporin levels suggest this to be a potentiation of cyclosporin nephrotoxicity rather than an effect of RAD001 itself.

1.4.4 Phase 1 study in oncology (Protocols 2101, 2102)

Clinical studies of RAD001 in Oncology have been ongoing since 2002. Because of the anticipated long pharmacodynamic (PD) effect (as shown in preclinical studies by the prolonged inhibition of downstream markers in tumor and other tissues) the first phase 1 study investigated RAD001 administered weekly. For reasons described below the phase 1 program has been extended to explore daily dosing also. The phase 1 program investigates the effects of dose and schedule on safety and pharmacokinetics as well as the pharmacodynamic effects in order to identify an optimal biological dosage (OBD). The OBD is defined as the minimum dosage of RAD001 resulting in target inhibition and which is satisfactorily safe. This program is still ongoing. A certain number of combination studies have also been initiated, and are summarized in the [Investigator's Brochure].

RAD001C: Protocols 2101/2: Steady-state pharmacokinetics (whole blood)

Parameter	5 mg/week	10 mg/week	20 mg/week	30 mg/week
N	4	4	2 ²	5
t _{max} (h)	1 (1-2)	1 (1)	1 (1)	2 (1-2)
C _{max} ^{ss} (ng/ml)	32.3 ± 15.4	69.0 ± 8.1	93.5 ± 0.4	80.0 ± 19.7 ¹
C _{max} ^{ss} /Dose (ng/ml/mg)	6.5 ± 3.1	6.9 ± 0.8	4.7 ± 0.0	2.7 ± 0.71
AUC _τ ^{ss} (ng·h/ml)	283 ± 48	573 ± 258	1001 ± 301	1798 ± 827
AUC _τ ^{ss} /Dose (ng·h/ml/mg)	56.6 ± 9.7	57.3 ± 25.8	50.1 ± 15.1	59.9 ± 27.6
t _{1/2} (h)	26.3 ± 2.9	37.9 ± 13.6	30.5 ± 12.0	36.8 ± 6.1

Values are median (range) for t_{max} and mean ± standard deviation for all others.

1. Two values above the upper assay quantification limit of 100 ng/ml were omitted.
2. samples for PK measurement of 2 patients lost in transport.

1.4.4.1 Phase 1 single agent studies (protocols 2101/2102, 2106 and 2107)

Two phase 1 studies (2101/2102 and 2107) are being conducted in patients with advanced solid cancers in whom the treatment may prove therapeutic. Study 2106 investigates the PD activity of RAD001 in a setting (4 weeks treatment pre-resection of newly diagnosed prostate cancer) in which the treatment cannot be expected to be therapeutic. The studies are open-label, sequential cohort studies in which the dosage of RAD001 is escalated from one cohort to the next according to the presence or absence of patients with dose-limiting toxicity (DLT). More details on these studies are included in the [Investigator’s Brochure].

1.4.4.2 Safety findings

All adverse events occurring in more than 10% of patients in studies 2101/2, 2106 and 2107 are summarized by schedule and dosage (according to the NCI Common Terminology Criteria, version 3) in Table 1-2.

Suspected adverse drug reactions (ADR) occurring in ≥10% of patients are summarized in Table 1-3. In order of frequency these include: rashes (37%), stomatitis/mucositis (27%), fatigue (26%), headache (19%), nausea (12%), diarrhea (10%) and vomiting (10%). The majority of suspected ADRs were of mild to moderate severity (CTC grade 1-2) with only isolated grade 3 events. The data suggest dose-relationship for rash, stomatitis/mucositis and fatigue.

The most frequently-reported ADR was rash &/or erythema. Mostly the nature of the rash was not specified. Descriptions were given for 7 patients: macular &/or papular (n=4), erythematous (n=2), acneiforme (n=1), pustular (n=1), pruritic (n=4), associated with dry skin in 3 cases. Rash was always grade 1-2. The localization was given for 16 patients, this involved: face/neck (n=9), upper limbs (n=6), lower limbs (n=6), trunk/back/buttocks (n=4). In 4 patients the rash was generalized (≥3 zones involved). Events reported as mucositis, stomatitis or mouth ulceration, were grade 1-2 in all but four patients. Grade 3 stomatitis occurred in 2 patients at 70mg/wk and in one patient

each at 50mg/wk and 10mg/d. It is the main dose-limiting toxicity.

Table 1-2 All adverse events in greater than or equal 10% of patients (grade 3-4 in brackets) Phase 1 monotherapy studies (June 04)

Weekly regimen							Daily regimen	Total	
No of patients	5mg	10mg	20mg	30mg	50mg	70mg	5mg	10mg	
Study 2101/2	4	4	5	5	6	7	4	6	41
Study 2107	0	0	8	0	6	7	6	6	33
Study 2106	0	0	0	4	1	0	4	1	10
Total	4	4	13	9	13	14	14	13	84
Weekly regimen							Daily regimen	Total	
Reported events									
Rash (all) ₁	0	0	1	3	7	7	8	8	34
Fatigue	1	0	7(1)	4	6(1)	4(1)	4(1)	6	32(4)
Headache	1	2	3	3(1)	6	4	5	3	25(1)
Stomatitis/mucositis	0	0	2	3	4(1)	5(2)	4	5(1)	24(4)
Nausea	3(1)	2	2	2	3	4(1)	2	2	20(2)
Anorexia	3	0	1	1	4	2	1	3	15
Constipation	2	0	2	1	1	2	4	2	14
Diarrhea	2	0	0	1	7	0	1	2	13
Vomiting	3	0	1	1	4	2	0	2	13
Cough	0	1	2	2	3	2	1	2	13
Dyspnea NOS	2	0	2	2(1)	3(1)	2(1)	1(1)	1(1)	13(5)
Abdominal pain NOS	3	0	1	0	1	0	2	2	9
Pruritus	0	1	1	2	1	0	3	1	9
Pyrexia	1	1	1	2	1	0	1	2	9
Back pain	1	1	0	1	3	0	1	1	8
Abdominal distension	0	0	0	0	3	1	1	3	8

1. Rash (all) includes: all types of reported rash & erythema

Table 1-3 Suspected adverse drug reactions¹ in greater than or equal 10% of patients (grade 3-4 in brackets) Phase 1 monotherapy studies (June 04)

No of patients	Weekly Regimen						Daily Regimen		Total
	5mg	10mg	20mg	30mg	50mg	70mg	5mg	10mg	
Study 2101/2	4	4	5	5	6	7	4	6	41
Study 2107	0	0	8	0	6	7	6	6	33
Study 2106	0	0	0	4	1	0	4	1	10
Total	4	4	13	9	13	14	14	13	84
Reported events									
Rash (all) ²	0	0	2	2	5	7	7	8	31
Stomatitis/mucositis	0	0	2	3	3(1)	5(2)	3	5(1)	23(4)
Fatigue	1	0	2	4	5	4	0	6	22(1)
Headache	0	0	1	3	3	2	5	2	16
Nausea	2	1	1	1	2	1	1	1	10
Diarrhea NOS	0	0	0	1	5	0	0	2	8
Vomiting NOS	2	0	1	1	2	1	0	1	8

1 Suspected drug-causality according to investigators.

2 Rash (all) includes: all types of reported rash & erythema

The data described below reflect exposure to everolimus (n=274) and placebo (n=137) in a randomized phase III study for the treatment of metastatic renal cell carcinoma. In total, 165 patients were exposed to everolimus 10 mg/day for ≥4 months. The median age of patients was 61 years (range 27 to 85). The most common adverse reactions (incidence ≥10%) were stomatitis, rash, fatigue, asthenia, diarrhea, anorexia, nausea, mucosal inflammation, vomiting, cough, peripheral edema, infections, dry skin, epistaxis, pruritus, and dyspnoea. The most common grade 3-4 adverse reactions (incidence ≥2%) were infections, stomatitis, fatigue, and pneumonitis.

The median duration of blinded study treatment was 141 days (range 19 to 451) for patients receiving everolimus and 60 days (range 21 to 295) for those receiving placebo. The rates of treatment-emergent adverse reactions resulting in permanent discontinuation were 7% and 0% for the everolimus and placebo treatment groups,

respectively. Most treatment-emergent adverse reactions were grade 1 or 2 in severity. Grade 3 or 4 treatment-emergent adverse reactions were reported in 39% versus 7% of patients receiving everolimus and placebo, respectively. Deaths due to acute respiratory failure (0.7%), infection (0.7%), and acute renal failure (0.4%) were observed on the everolimus arm.

Everolimus has immunosuppressive properties and may predispose patients to bacterial, fungal, viral or protozoan infections, including infections with opportunistic pathogens. Localized and systemic infections, including pneumonia, other bacterial infections, invasive fungal infections, such as aspergillosis or candidiasis and viral infections including reactivation of hepatitis B virus, have been described in patients taking everolimus. Some of these infections have been severe (e.g. leading to respiratory or hepatic failure) and occasionally have had a fatal outcome.

Physicians and patients should be aware of the increased risk of infection with everolimus. Treat pre-existing infections prior to starting treatment with everolimus. While taking everolimus, be vigilant for symptoms and signs of infection; if a diagnosis of infection is made, institute appropriate treatment promptly and consider interruption or discontinuation of everolimus. If a diagnosis of invasive systemic fungal infection is made, discontinue everolimus and treat with appropriate antifungal therapy.

Reactivation of Hepatitis B (HBV) has been observed in patients with cancer receiving chemotherapy (Yeo 2004). Sporadic cases of Hepatitis B reactivation have also been seen in this setting with everolimus. Use of antivirals during anti-cancer therapy has been shown to reduce the risk of Hepatitis B virus reactivation and associated morbidity and mortality (Loomba 2008). A detailed assessment of Hepatitis B/C medical history and risk factors must be done for all patients at screening, with testing performed prior to the first dose of everolimus.

Hypersensitivity reactions manifested by symptoms including, but not limited to, anaphylaxis, dyspnea, flushing, chest pain or angioedema (e.g. swelling of the airways or tongue, with or without respiratory impairment) have been observed with everolimus.

Hyperglycemia has been reported in clinical trials. Monitoring of fasting serum glucose is recommended prior to the start of everolimus therapy and periodically thereafter. Optimal glycemic control should be achieved before starting a patient on everolimus. Mouth ulcers, stomatitis and oral mucositis have been seen in patients treated with everolimus. In such cases topical treatments are recommended, but alcohol- or peroxide-containing

Elevations of serum creatinine, usually mild, have been reported in clinical trials. Monitoring of renal function, including measurement of blood urea nitrogen (BUN) or serum creatinine, is recommended prior to the start of everolimus therapy and periodically thereafter.

Decreased hemoglobin, lymphocytes, platelets and neutrophils have been reported in clinical trials. Monitoring of complete blood count is recommended prior to the start of everolimus therapy and periodically thereafter.

Everolimus is not recommended in patients with severe hepatic impairment, (Child-Pugh class C).

The use of live vaccines and close contact with those who have received live vaccines should be avoided during treatment with everolimus.

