5.3 Dose modifications / Management of Adverse Reactions

Toxicity will be assessed using the NIH-NCI Common Terminology Criteria for Adverse Events, version 3.0 (CTCAEv3.0, (<http://ctep.cancer.gov/forms/CTCAEv3.pdf>)).

Dose Modification Table:

Dose level	-2	-1	0
RAD001	Off study	5 mg daily	10 mg daily
Letrozole	Off study	2.5 mg daily	2.5 mg daily

Patients will be removed from study for any:

- grade 4 treatment-related toxicity (assuming that appropriate preventive therapy has been given where possible – e.g. antiemetic therapy in case of vomiting, lipid-lowering drug in case of hyperlipidemia), or
- hematologic or non-hematologic toxicity requiring interruption of one or both drugs for > 3 weeks. For detailed recommendations on dose interruption and modification due to suspected toxicity, please refer to the following table.

**Algorithm for interpretation and dose modification
 due to suspected treatment related toxicity:**

Treatment-related toxicity	Actions
Non-hematological toxicity	
Grade 2 (except fatigue, hyperlipidemia, and non-infectious pneumonitis – see Dose Modification Table, page 30)	For first occurrence, interrupt RAD001 (continue letrozole) until recovery to grade ≤ 1 then reintroduce RAD001 (no dose reduction). If the event recurs, interrupt study treatment (Letrozole and RAD001) until recovery to grade ≤ 1 then reintroduce therapy at -1 dose level. If the event recurs a 3 rd time, remove patient from study.
Grade 3 (except hyperlipidemia and non-infectious pneumonitis)	For first occurrence, interrupt study treatment (Letrozole and RAD001) until recovery to grade ≤ 1 . Then reintroduce therapy at -1 dose level. If the event recurs remove from study. For pneumonitis consider the use of a short course of corticosteroids.
Grade 4	Remove from study.

Lipid-lowering drugs

Increased lipid levels are a known adverse effect of treatment with both RAD001 and aromatase inhibitors. In case of hyperlipidemia (\geq grade 1 hypercholesterolemia with or without hypertriglyceridemia), in addition to dietary advice to patients, an HMG-CoA reductase inhibitor such as atorvastatin, pravastatin or fluvastatin may be associated with study treatment.

Hematological toxicity	

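### The dose-modification table in Section 5.3 restarts everolimus after an invasive systemic fungal infection for which Section 1.4.4.2 says to discontinue it

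*Combined protocol and SAP*

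**What the plan says.** Section 1.4.4.2 warns that everolimus is immunosuppressive and lists infections seen with it, invasive fungal infections among them. It adds: "Some of these infections have been severe (e.g. leading to respiratory or hepatic failure) and occasionally have had a fatal outcome." For infection in general it asks physicians to treat and to consider either interrupting or discontinuing everolimus. For one diagnosis it is firmer: "If a diagnosis of invasive systemic fungal infection is made, discontinue everolimus and treat with appropriate antifungal therapy."

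Section 5.3 refers sites to a table for the detail of dose interruption and modification when toxicity is suspected to be treatment-related. Two non-hematological rows matter here:

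- The row headed "Grade 2 (except fatigue, hyperlipidemia, and non-infectious pneumonitis" has the action "For first occurrence, interrupt RAD001 (continue letrozole) until recovery to grade" 1 or better, "then reintroduce RAD001 (no dose reduction"). A second event is restarted at level -1, and a third takes the patient off study.
- The row headed "Grade 3 (except hyperlipidemia and non-infectious pneumonitis") has both drugs held until recovery to grade 1 or better. "Then reintroduce therapy at -1 dose level. If the event recurs remove from study."

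The dose table sets level 0 at RAD001 10 mg daily and level -1 at 5 mg daily, with letrozole 2.5 mg at both; the next step down is off study. Patients also leave the study for grade 4 treatment-related toxicity and for "hematologic or non-hematologic toxicity requiring interruption of one or both drugs for > 3 weeks." The last row of the table puts that limit at 3 weeks or more.

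**The concern.** Invasive systemic fungal infection is not among the exceptions in either row, so the general grade rules apply to it. A site that doses from the table would give an immunosuppressant again after an infection for which the protocol elsewhere says to stop it. The table's trigger for restarting is recovery to grade 1 or better, not completion of antifungal treatment. A site that follows Section 1.4.4.2 avoids the problem, so the risk falls on a patient whose site works from the table alone.

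**Working it through.** No figure in the plan needs reproducing. The check is a side-by-side reading of Section 1.4.4.2 and Section 5.3, followed by a search for anything that reconciles them.

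**Step 1: trace the two texts.** Take a patient on 10 mg with a treatment-related invasive systemic fungal infection that returns to grade 1 or better in under 3 weeks, unless the row says otherwise.

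| Case | Section 1.4.4.2 | Section 5.3 table | Difference in daily everolimus |
|---|---|---|---|
| First grade 3 event | Discontinue | Restart at level -1, 5 mg | 5 - 0 = 5 mg |
| Recurrent grade 3 event | Discontinue | Off study | None |
| First grade 2 event (assumed possible) | Discontinue | Restart at 10 mg | 10 - 0 = 10 mg |
| Second grade 2 event (assumed possible) | Discontinue | Restart at level -1, 5 mg | 5 - 0 = 5 mg |
| Third grade 2 event (assumed possible) | Discontinue | Off study | None |
| Grade 4 event | Discontinue | Off study | None |
| Interruption longer than 3 weeks | Discontinue | Off study | None |

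The texts disagree in three cells. The grade 2 cells are conditional because grading follows CTCAE v3.0, which the protocol cites by link and does not reproduce. A hold of exactly 3 weeks is ambiguous, since the text and the table differ on whether 3 weeks itself counts.

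**Step 2: is 'discontinue' a temporary hold?** The preceding sentence of Section 1.4.4.2 names interruption and discontinuation as separate options. Sections 5.3.2 and 5.3.3 make the same distinction. For hepatitis B reactivation, study drug is interrupted and restarted if resolution comes within 28 days, and discontinued if later. For hepatitis C reactivation it is simply discontinued. One usage points the other way: Section 5.3.1 says everolimus should be discontinued for grade 3 pneumonitis and then expressly allows it to be restarted at a lower dose. Section 1.4.4.2 contains no such allowance.

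**Step 3: does another section override the table?** Sections 5.3.1 to 5.3.3 cover pneumonitis, hepatitis B and hepatitis C. None covers fungal infection.

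Section 5.3.5 restricts everolimus alongside azoles. Strong inhibitors are to be avoided: ketoconazole and itraconazole are named, Table 3-6 adds posaconazole, and a footnote treats voriconazole as strong. With fluconazole, a moderate inhibitor, the dose is halved (10 / 2 = 5 mg) and returns to its previous level when fluconazole stops. These are co-administration rules and do not say whether everolimus may resume after the infection. The conflict remains with a non-azole antifungal, with fluconazole, and when a strong azole ends inside the 3-week limit. For a patient restarted at 5 mg while on fluconazole, halving gives 5 / 2 = 2.5 mg, below the lowest level in the dose table. Section 5.3.5 mentions alternate-day dosing, so the outcome of that branch is unclear.

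Section 4.4 allows removal for unacceptable toxicity or in the physician's judgement. It does not mention fungal infection.

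**The case against.** The strongest reply is that the texts can be read together. Section 1.4.4.2 is specific to one diagnosis, the table is general, and a specific instruction ordinarily governs. Section 4.4 gives the physician a route to stop. These arguments show that a careful site can comply; they do not correct the table. The protocol has no statement of precedence, and Section 5.3 sends sites to the table for detail. If Section 1.4.4.2 is mere background, the operative section has no safeguard for this infection.

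It can also be argued that permanent discontinuation exceeds the 3-week interruption limit, so that the table itself ends in removal. That is circular, because the table ends the interruption at recovery to grade 1 or better.

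Three objections stand and limit the point. First, the pneumonitis text shows that discontinuation is not always final in this protocol. A reader might infer that Section 1.4.4.2 forbids restarting in so many words; it does not, and permanence is an inference from its contrast with interruption and from the absence of a restart clause. Second, a reader might take a return to 10 mg as the main case. Nothing in the documents shows that this diagnosis can be grade 2, so the firm contrast is 5 mg against none. Third, the documents do not show how often such a case would recover inside 3 weeks. In the phase 1 single-agent data (Section 1.4.4.3), the only serious and only grade 3 infection among 84 patients was a pneumonia, and the fungal events itemised were three reports of oral candidiasis.

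**Conclusion.** The conflict is real and should be corrected. It is established for a treatment-related first grade 3 event that recovers to grade 1 or better in under 3 weeks: the table gives 5 mg daily where Section 1.4.4.2 gives none. At grade 2 it is conditional on such a grade being possible, with 10 mg against none after a first event and 5 mg against none after a second. The finding rests on reading discontinuation as permanent, which is the better reading but not the explicit wording.

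A reader might infer that a predictable number of patients would be re-exposed. The documents do not support that. They give no rate for this infection, and the 0.7% of infection deaths on everolimus in the phase III renal trial covers infections of all kinds. With at most 42 patients, the number affected may be zero. The case for acting rests on the severity of the outcome and the small cost of the correction. Neither the stopping rule nor its operating characteristics change.

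**What to change.** Except invasive systemic fungal infection from the grade 2 and grade 3 non-hematological rows of the Section 5.3 table, and add a row to this effect: *Invasive systemic fungal infection, any grade: stop everolimus, do not reintroduce it, and give suitable antifungal treatment; this row prevails over the grade rows.*

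The new row should also settle letrozole. Section 1.4.4.2 stops only everolimus, and the first grade 2 action already continues letrozole alone during a hold, but the dose table has no letrozole-alone level. The sponsor should state whether the patient stays on letrozole or comes off study.

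The cost is one new row and an exception in two existing rows at the next amendment, with no added visits or tests. The downside is that a patient who might have been rechallenged stops everolimus. If she comes off treatment before response is established, Section 10.1 makes her evaluable for toxicity only, and she might be replaced. That would use 1 of the 7 replacements foreseen in Section 10, so the cap of 35 + 7 = 42 stands.
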